The first provider will dispose of the gloves and device. The first provider will then leave the hospital room. S/he will not speak to the second provider.

The second provider will enter the hospital room. The second provider will introduce him/herself to the patient and explain that s/he is going to perform a cervical examination. The trial coordinator will record the time of the second exam. The second exam must be completed within 10 minutes of the first exam. The second provider will complete a cervical examination as above using a DilaCheck® device. The second provider and trial coordinator will repeat the same steps as described above for the first provider. The second provider will leave the room.

Patient Survey. The trial coordinator will then ask the patient to answer the questions on the Patient Survey. The survey will elicit relevant biological and demographic variables including age, race, ethnicity, gestational age, weight, and use of epidural anesthesia. It will assess the patient's discomfort with the examinations, confidence in the accuracy of the measurements, and satisfaction with the examinations. Patients will be asked to report any side effects they experienced and to provide any comments they have.

Patient Reimbursement. The trial coordinator will offer the patient a \$25 gift certificate to thank her for participating. The patient will sign a receipt to confirm that she received the gift certificate.

Provider Survey. At the end of the trial, the trial coordinator will ask all participating providers to complete the Provider Survey. The survey will elicit the provider's years of experience, role on Labor and Delivery, opinions about inter-examiner agreement using standard methods and using DilaCheck®, and ease of use and satisfaction with the device. The survey will ask whether providers experienced any adverse events and if their patients experienced any adverse events during the trial. They will have the option to provide comments.

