Another potential problem is clinician participation. Clinicians will be incentivized to participate through the potential for inclusion in the publication and an appeal to the greater good of scientific research and the betterment of our management of labor and delivery. TJU has an excellent record of clinician participation in trials. A related potential problem is training clinicians in using the device. In the prior simulator trial, device training was accomplished in less than one minute, but in this trial we will dedicate more time to training as well as testing the accuracy of the clinician during the training using simulators. The Sponsor will travel to TJU and provide trainings.

Benchmarks. Benchmarks include training at least two hospital providers to use the device and enrolling at least 6 patients monthly. If any of these benchmarks is lagging behind estimates, the Sponsor will consult with the hospital to create a plan to address the issue.

PROTECTION OF HUMAN SUBJECTS

Human Subjects. This clinical trial necessitates the involvement of human subjects in order to validate the novel medical device for use in humans. The prior simulator trial verified the concept, but until a trial is conducted in humans, the true value of the device is unknown. Furthermore, it is of the utmost importance to study the device in a setting

with strict procedures in place to monitor for serious or unexpected adverse events. The trial will comply with federally mandated regulations per 45 CFR 46.

Institutional Host. TJU Hospital will physically host the study, provide patients for potential enrollment, and provide the hospital providers to complete the cervical examinations. We will obtain approval from the TJU IRB prior to enrollment. The trial coordinator is a TJU employee and will work with Labor and Delivery staff to schedule appropriate times to enroll patients and collect data.

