Involvement and Characteristics of Human Subjects. The subject population is women presenting to the hospital for evaluation of a diagnosis of labor and women admitted to the hospital Labor and Delivery unit for management of the first stage of labor. Planned enrollment is 50 patients. The subject population is reproductive aged, pregnant women with stable health. In order to be eligible for the trial, a woman must have a term pregnancy (≥ 37 weeks gestation) and be able to complete informed consent. Only patients presenting to or admitted to the Labor and Delivery unit for management of labor are eligible. For instance, a patient presenting to her clinician's office for a routine prenatal appointment is not eligible, or a patient admitted to the Labor and Delivery unit for a scheduled cesarean section who is not in labor is also not eligible. Exclusion criteria include advancement to the second stage of labor, any condition that renders labor unsafe for the patient, and any other condition that necessitates an emergent or urgent cesarean section. This will ensure exclusion of patients with unstable medical situations. This clinical trial necessarily involves the participation of a vulnerable population, pregnant women, because the device is intended for use in pregnant women. All of the conditions outlined in 45 CFR part 46 Subpart B are met.

Sources of Research Material. This trial does not use any biological samples or hazardous materials. The data collected from human subjects includes: records of two cervical dilation measurements, photograph of the device reading, age, race, ethnicity, gestational age, weight, discomfort ratings, epidural status, confidence in accuracy, patient satisfaction, side effects, and comments. The data collected from providers includes: beliefs about agreement of standard cervical dilation measurements, beliefs about agreement of measurements with DilaCheck®, years of experience on Labor and Delivery, role on Labor and Delivery, provider side effects, patient side effects, ease of use of the device, satisfaction with the device, and comments.

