Risks Related to the Study Device. To protect patients against any risk from exposure to the device, the devices will be manufactured under Design Controls and Good Manufacturing Practices, and documentation of biocompatibility and sterility testing of all components can be made available prior to their use. The device was designed to maximize safety and comfort with all soft, medical grade components. The manufacturer tests the devices for reliability. If the device fails in any way, both the trial coordinator and the provider will confirm that all components have been removed fully from the patient. To minimize risk from using a previously untested device, the results of the examinations will not be used in patients' clinical care.

Discomfort. Patients will be reminded that they may withdraw from the study at any time, including after the first examination if they found it too uncomfortable to consent to a second examination. Providers will minimize discomfort through standard techniques such as confirming that the patient would like to continue the procedure before and during an examination. Most women receive epidurals in labor and are thus unlikely to have pain with examinations.

Increased Risk of Infection. The connection between cervical examinations and infection is controversial. Theoretically, insertion of anything into the vagina, even a sterile gloved finger, could introduce bacteria and cause maternal fever and chorioamnionitis. However, recent research has failed to support this theory. For instance, a 2012 trial of 2,395 women revealed no association between number of cervical examinations and intrapartum maternal fever.⁶ Therefore, an additional examination confers at most minimal additional risk of infection to the patient. The device is sterilized using gamma radiation, and we will complete confirmatory testing of sterilization methods prior to shipping the device from the manufacturer.

Unintentional Amniotomy. Unintentional amniotomy is equally likely with the

device and with standard methods since the device has all soft components. If amniotomy is planned, it will be carried out following the two examinations in order to reduce the theoretical risk of infection with examinations following rupture of membranes.

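### The protocol describes no systematic follow-up, after the immediate post-exam survey, for the infection and membrane-rupture risks it names

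*Combined protocol and SAP*

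**What the plan says.** **Outcome and purpose.** The Protocol Summary lists documentation of adverse events among the secondary outcomes. Under Protection of Human Subjects (Human Subjects), the protocol stresses studying the device in a setting with "strict procedures in place to monitor for serious or unexpected adverse events". Protection of Vulnerable Populations gives safety, with efficacy, as a purpose of the research.

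**Named risks.** Potential Risks of Study Participation includes a theoretical infection risk and membrane rupture. Increased Risk of Infection says that insertion of anything into the vagina "could introduce bacteria and cause maternal fever and chorioamnionitis", and calls the link controversial. On the other risk, the protocol states: "Unintentional amniotomy is equally likely with the" device as with standard methods.

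**Patient-level collection.** In Data Collection, "The second exam must be completed within 10 minutes of the first exam". Then, under Patient Survey, "The trial coordinator will then ask the patient to answer the questions on the Patient Survey", and on safety: "Patients will be asked to report any side effects they experienced and to provide any comments they have". Only the gift certificate follows. In Sources of Research Material, the patient items end with "discomfort ratings, epidural status, confidence in accuracy, patient satisfaction, side effects, and comments".

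**Other routes.** On the Provider Survey: "The survey will ask whether providers experienced any adverse events and if their patients experienced any adverse events during the trial". That section places the survey at the close of the whole trial; Risks to Providers places the survey given to providers at the close of each trial session. TJU IRB Review requires serious events to be reported within a week of the investigator learning of them. DSMB Review has the Sponsor send a monthly list of adverse events.

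**The concern.** The timing of the one patient-level question does not match the harms the protocol itself names. A question asked minutes after the exams suits discomfort, or a rupture noticed at the time. It does not suit fever or chorioamnionitis, which I assume would not show within minutes of an exam, or a rupture that follows later in labor.

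At stake is a stated secondary outcome. The adverse-event lists sent to the DSMB, and the results due on ClinicalTrials.gov, could be nearly empty for infection whatever happened to the women. The statement that unintentional amniotomy is equally likely in both arms could not be checked either. Intact membranes are an entry criterion, but no field shows whether they were still intact after each exam.

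**Working it through.** The plan states no figure for safety follow-up, so there is none to reproduce. The check is a reading of every section on adverse events, followed by a short calculation of scale.

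**1. Which route could record which event**

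| Event | Patient Survey | Provider Survey at session end | Provider Survey at trial end | Serious-event reporting |
|---|---|---|---|---|
| Rupture noticed during an exam | Yes, if mentioned | Yes, if mentioned | From memory | Only if serious and known |
| Later unintended rupture | Too early | Mostly too early | From memory, if the provider knew | Only if serious and known |
| Later non-serious fever | Too early | Mostly too early | From memory, if the provider knew | No |
| Chorioamnionitis | Too early | Mostly too early | From memory, if the provider knew | Only if serious and known |

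Session length is not stated, hence ‘mostly’.

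**2. The Provider Survey under each stated timing**
- *End of the trial.* The Protocol Summary plans enrollment over one year. At the Benchmarks minimum of 6 patients a month, 50 women take 50 / 6 = 8.3 months. A provider could thus be recalling an exam from 8 to 12 months earlier. The survey could not feed the monthly DSMB lists while the trial runs, and its described content has no link to a subject number or arm.
- *End of a session.* Recall is fresh, but later events have mostly not yet happened.
- Under either timing, nothing requires the examining provider to have followed the woman after the exam.

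**3. Data fields.** The patient list in Sources of Research Material has side effects as a general item. It has no temperature or fever, no chorioamnionitis, no membrane status after an exam, and no time or cause of rupture. The provider list has patients' side effects, again as a general item.

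**4. Scale.** The documents give no rate of intrapartum fever. I assume 2% to 10% as a background rate in all 50 women, from any cause.
- Expected events: 50 × 0.02 = 1; 50 × 0.10 = 5.
- Chance of at least one: 1 − 0.98^50 = 0.64; 1 − 0.90^50 = 0.99.

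**5. What zero events would mean with complete follow-up.** The one-sided 95% upper bound for zero events in n women is 1 − 0.05^(1/n).
- n = 25 (one arm): 1 − 0.05^(1/25) = 11.3%.
- n = 50 (both arms): 1 − 0.05^(1/50) = 5.8%.

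These bounds hold only if every woman is followed and every event recorded. Without that, zero reports give no usable bound.

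**The case against.** A reader might infer that the Patient Survey is the only patient-level source and that later events cannot be recorded at all. The documents do not support that. The Provider Survey asks about patients' adverse events, serious events have a reporting route that does not depend on any survey, and the DSMB receives monthly lists. A rupture during an exam could be noted at once: the coordinator attends the exams and the patient is asked straight afterwards. This objection stands, and it limits the point to events that arise later and to the lack of a specific field.

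The risk is also described as small. The protocol calls the infection risk theoretical and cites a study of 2,395 women that found no association between number of exams and intrapartum fever. Both arms have two exams. The fever rate assumed above counts background events, so 1 to 5 of 50 does not measure harm from the device. All of this stands. It lowers the urgency but does not remove a stated secondary outcome.

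A reader might also infer that the plan will claim safety from an empty list. No section says so: Statistical Analysis has adverse-event descriptions reviewed individually, with no between-arm safety test. The warning concerns how few reports could be read, not a conclusion the plan draws.

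Finally, the monitoring plans promised to the IRB and the NICHD are not in the documents, and the consent pages were removed. Follow-up or chart access may be covered there. That stands as a limit on this point, which concerns the protocol as it reads.

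**Conclusion.** The point holds in a limited form. The protocol describes no systematic follow-up after the post-exam survey for the infection and membrane-rupture risks it names. Later events depend on awareness-based serious-event reporting or on a Provider Survey with two conflicting timings. Later non-serious events will be under-recorded in both arms, and few reports could not be taken as evidence of safety.

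The size is modest: about 1 to 5 background fever events among 50 women, if the assumed 2-10% rate is right, many of them likely to go unrecorded. The conclusion also assumes that infection would not show within minutes of an exam, and that no supplementary monitoring plan already sets out follow-up. The primary outcome is not affected. With 25 women per arm, better collection would give a complete record, not a comparison of the arms.

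**What to change.** - State an adverse-event window and source in the protocol, identical in both arms.
- Have the trial coordinator record membrane status after each of the two exams.
- At discharge, abstract from the chart dated intrapartum fever, dated chorioamnionitis, and the time and cause of membrane rupture. Keep planned amniotomy separate from unintended rupture, because the Unintentional Amniotomy section allows a planned amniotomy after the exams.
- List these events by arm, descriptively, in the DSMB and final reports, with no between-arm test.
- Add the items to Sources of Research Material, and to the consent wording if chart access is not already covered.
- Reconcile the timing of the Provider Survey between the Provider Survey and Risks to Providers sections.

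The cost is one short abstraction form for 50 charts and possibly a consent or IRB wording change. The coordinator is already a TJU employee, and no new patient procedure is needed.

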The proposed study tests the novel DilaCheck® device *in vivo*. The target population is women presenting to the hospital for evaluation of labor or admitted to the Labor and Delivery unit for management of the first stage of labor. The Sponsor (Elm Tree Medical Inc.) trains providers working on the Labor and Delivery unit in the use of DilaCheck®. After informed consent, each patient participant is randomized to receive either two cervical dilation examinations with standard methods or two cervical dilation examinations using the device. Two practitioners complete the cervical examinations separately. The primary outcome is inter-examiner agreement between the control and device arms. Secondary outcomes include agreement of subjective measurements with DilaCheck® measurements over time, agreement of providers' device readings with a blinded reviewer's, patient and provider satisfaction, and documentation of adverse events. Planned enrollment is 50 participants over one year. We hypothesize that the device will increase agreement between the two practitioners from about 49% to 90%, as demonstrated in the simulator trial. The long-term objective is to validate DilaCheck® for use in increasing precision in cervical dilation measurements so that this tool may be available to Labor and Delivery providers to enhance quality of care for pregnant mothers. Increased precision in cervical dilation measurements will enable providers

to make better recommendations for admission to the hospital, augmentation or induction of labor, and cesarean section.

The proposed study is a randomized, controlled trial comparing inter-examiner agreement of standard methods for measuring cervical dilation to a novel medical device. The research population is pregnant women in the first stage of labor.

TRIAL PROTOCOL

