Inconvenience. Providers will not pressure patients into participating and will clearly inform them that participation is entirely optional and will have no effect on care. The trial will be carried out in an efficient manner with attention paid to minimizing use of the providers' and patients' time.

Risks to Providers. If the Labor and Delivery unit is too busy, providers may opt out of participation for that shift. The study will monitor for any adverse events experienced by the provider through the survey given to all providers at the end of a trial session.

Protection of Vulnerable Populations. This trial meets all conditions as listed in 45 CFR part 46 Subpart B. A simulator trial was conducted as a preclinical study to provide data prior to testing the device with pregnant women. Documentation of sterility and biocompatibility testing of the device materials *in vitro* can be made available prior to use in the trial. There is minimal risk to the fetus, and these risks have been minimized as much as possible for achieving the objectives of the research. The device holds the prospect of direct benefit to both pregnant women and fetuses. The purpose of the research is the development of important biomedical knowledge: determination of the efficacy and safety of this novel device that cannot be obtained by other means. Researchers will obtain consent from every patient in accordance with the informed consent provisions of 45 CFR 46 Subpart A. No pregnancies will be terminated. There is no contact with neonates.

Potential Benefits of the Proposed Research to Human Subjects and Others.

Human subjects will benefit from participating in the research through their receipt of education on cervical dilation examinations via the consent process and through the knowledge that they have contributed to the care of future laboring women. Providers will benefit from participation through receiving individualized training in the use of the device, through gaining experience in clinical trials, and through the option to participate in editing the scholarly journal article in exchange for authorship. Because patients are exposed to a non-significant level of risk by participating in the study, the benefits to them, to providers, and to the field of obstetrics and future laboring mothers outweighs the risks.

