Importance of the Knowledge to be Gained. The greatest benefit of the proposed research is the validation of a new device that could revolutionize labor management. If successful in increasing inter-examiner agreement, DilaCheck® has the potential to increase certainty in the management of labor, decrease length of admissions to the Labor and Delivery unit, decrease unnecessary interventions and cesarean sections, and decrease the time a woman is in labor. Since the device is not anticipated to expose patients to any significant risks, this potential for a vast benefit to laboring mothers and newborns far outweighs the risks to participants.

DATA AND SAFETY MONITORING PLAN

TJU IRB Review. We will submit a detailed monitoring plan to the TJU IRB for review and approval prior to initiation of the trial. All serious adverse events (AEs) will be reported to the TJU IRB within one week of the investigator becoming aware of the event. Any unanticipated problems will be reported to the TJU IRB within two weeks. The TJU IRB also requires interim reviews of the trial, either every six or 12 months, as determined by the IRB upon initial review of the protocol. The continuing review is submitted through completion of the "Continuing or Final Review of Research Protocols Involving Human Subjects" form. It includes enrollment data, adverse event reporting (including identification of adverse events not anticipated in the consent form), increased risks identified since the last review, demographics of enrolled patients, withdrawal of patients, loss to follow up, subject complaints, protocol changes, interim findings, assurance of an up-to-date literature review by the PI, changes to FDA status, and conflicts of interest. We will submit this form to the TJU IRB every six or 12 months, per the IRB's designation.

Sponsor Review. The Sponsor will review all data collected from the prior month at the beginning of each month. If there are serious AEs, she will report them to the necessary institutions.

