DSMB Review. The DSMB consists of four volunteer experts in the following fields: obstetrics, clinical trials, law, and ethics. Because they are volunteers, they do not stand to benefit from continuing the trial if it is not in the best interest of participants. The Sponsor will compile a document with enrollment data, lists of all adverse events, and summary statistics of data collected up to that date on a monthly basis. All information will be de-identified. The Sponsor will distribute the document via email to the members of the DSMB on the last Friday of each calendar month for the prior month's data. The DSMB members will review the document. If there are unexpected or serious AEs, the DSMB will determine whether continuation of the trial is safe. They will have the power to discontinue the trial at any time if they feel continuation is not in the best interest of patients. The Sponsor will be responsible for reporting a trial discontinuation due to safety concerns to the necessary regulatory bodies.

NIH/ Funding Institution & Center (IC). This trial has been accepted for funding from a STTR grant. The funding IC for this trial is the Eunice Kennedy Shriver National Institute of Child Health & Human Development (NICHD). The Sponsor will submit a monitoring plan to the NICHD Program Officer (PO) before the trial begins. During the trial, the Sponsor will inform the NICHD PO of any recommendations and activities that emanate from monitoring activities. The Sponsor will submit summary reports of the DSMB's discussions to the NICHD PO on a monthly basis as they become available. All

unanticipated problems and serious adverse events will be reported to the NICHD PO within one month of the IRB's receipt of the report of the problem from the Sponsor.

FDA. The FDA has cleared DilaCheck® as a Class 1 low risk device. The original device design was cleared by a 510(k) application. Because the current design represents such a low (non-significant) risk, it is considered Class 1 exempt and does not require FDA clearance of a 510(k) application prior to marketing. Pre-market obligations have been documented via a "Letter to File," and the device is registered with the FDA. The FDA has not withheld or restricted the device.

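### The protocol places the Provider Survey at two different times; if it is given at study end, adverse events known only through it miss the monthly safety reviews held during enrolment

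*Combined protocol and SAP*

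**What the plan says.** Five parts of the combined protocol and SAP bear on this.

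- **Trial Protocol, Provider Survey.** The timing is "At the end of the trial, the trial coordinator will ask all participating providers to complete the Provider Survey". The content includes adverse events: "The survey will ask whether providers experienced any adverse events and if their patients experienced any adverse events during the trial". The same form collects experience, role, views on agreement, ease of use and satisfaction.
- **Protection of Human Subjects, Risks to Providers.** Adverse events in providers are to be monitored "through the survey given to all providers at the end of a trial session". This sentence concerns providers' own events only.
- **Data and Safety Monitoring Plan, Sponsor Review.** "The Sponsor will review all data collected from the prior month at the beginning of each month".
- **Data and Safety Monitoring Plan, DSMB Review.** The sponsor compiles a document with enrolment data, "lists of all adverse events, and summary statistics of data collected up to that date on a monthly basis".
- **Protocol Summary.** "Planned enrollment is 50 participants over one year". Documentation of adverse events is listed there as a secondary outcome.

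**The concern.** The protocol describes one provider survey and gives it two times. Site staff cannot tell whether to hand it out once or after each session, and the choice decides whether its adverse-event answers exist when the monthly reviews take place. If the survey waits until study end, the sponsor and the DSMB work during enrolment from lists that are described as complete but lack whatever only the providers know.

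There is also a problem of attribution. Nothing in the design confines a provider to one arm, and the survey as described carries no Subject Number. A single answer about events over the whole trial could not be reliably assigned to a patient or to an arm, which weakens any comparison of adverse events between device and control.

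**Working it through.** The plan states no figure on this point. The check is a comparison of texts plus a count of reviews.

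**1. The two timings.**

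| Section | When the survey is given | Whose events |
|---|---|---|
| Provider Survey | End of the trial | Providers and their patients |
| Risks to Providers | End of a trial session | Providers only |

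**2. What the Provider Survey paragraph most likely means.** For a session reading: Trial Coordination uses the word trial loosely for a single session when it lists the people needed to run it, and the Provider Survey paragraph follows directly on the session steps. For a study-end reading: it addresses every participating provider rather than the two examiners, it asks about events over the whole trial, and it collects items that make sense once, such as experience and overall satisfaction. The Patient Survey, by contrast, is plainly placed straight after the examinations. The balance favours study end.

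**3. Other sources.** The Data Collection Form is described only as holding dilation readings. Sources of Research Material lists provider and patient side effects among the data obtained from providers, but names no other form or time. Risks Related to the Study Device has the coordinator and provider check that all components are out after a device failure, but specifies no record. Patients report side effects on the Patient Survey after the two examinations. TJU IRB Review gives serious events one week, counted from the investigator's awareness; no step from provider to investigator is described.

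What depends on the Provider Survey alone is therefore (a) providers' own events and (b) patient events that the provider noticed and the patient did not report.

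**4. Number of reviews affected.** Take one review per month of enrolment.

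- One-year plan (Protocol Summary): 12 months, so 12 reviews.
- Benchmark rate (Benchmarks): 50 patients / 6 per month = 8.3 months, so about 9 reviews.

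Each review covers the prior month's data, so the review of the final month falls just after enrolment closes. The number held strictly while patients are being examined may be one lower.

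**5. Result under each timing.** With the survey at study end, events of types (a) and (b) reach none of these reviews and appear at best in a report after the last examination. With the survey after each session, they are available for the next monthly review.

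**The case against.** The strongest reply is that the two paragraphs need not conflict. The protocol sometimes uses the word trial for a session, so the paragraphs may already agree, and a survey given after each session and again at study end would satisfy both. That stands: a reader might infer a flat contradiction in which only one instruction can be followed, and the documents do not support that. What remains is an ambiguity in a safety procedure, with the more natural reading being the less protective one.

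The second reply is that other routes exist. Patients report side effects at once, the coordinator attends the sessions, serious events are expedited, and nothing says the survey is the only way a provider may report. This also stands, and it narrows the exposed set to non-serious or unrecognised events that the provider alone knows of and does not volunteer. A reader might infer that adverse events in general could escape every safety review. The documents do not support that either: the Patient Survey feeds the monthly data, and a last report after study end could still list the survey answers.

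Third, the Risks to Providers sentence covers only providers' own events, for which the protocol expects no risk beyond that of a standard examination. This is correct. For patient events noticed by providers, the difficulty is not a clash of two timings. The only timing given is the Provider Survey's, and it appears to come too late for the monthly reviews.

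Finally, one might argue that each provider would have to recall a large number of device examinations. The documents do not give the number of providers, so no recall burden can be stated.

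**Conclusion.** The point holds in limited form and should be corrected. The two paragraphs give different timings for the only routine provider source of adverse events that is described. On the more natural reading of the Provider Survey paragraph, survey-only provider reports miss all the monthly sponsor and DSMB reviews held during enrolment: about 9 at the benchmark rate, 12 over the planned year. As described, they also cannot be tied to a patient or arm.

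This rests on three assumptions: that the Provider Survey paragraph means study end; that providers do not volunteer such events earlier; and that the survey form, which is not in the documents, carries no patient identifier. The primary outcome and the sample size are unaffected, and serious events keep their one-week IRB route once the investigator is aware.

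**What to change.** Reconcile the Provider Survey and Risks to Providers paragraphs so that both state the same two steps.

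1. **After each session**, each of the two providers answers two questions, with the Subject Number recorded: did you have an adverse event, and did you notice one in the patient? These can go on the existing Data Collection Form, and the answers enter the next monthly sponsor and DSMB review.
2. **At study end**, the Provider Survey keeps the experience, opinion, ease-of-use and satisfaction items, plus one catch-all adverse-event question for anything that came to light after a session.

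A further sentence in the Data and Safety Monitoring Plan should name the sources from which the monthly adverse-event list is compiled.

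The cost is a wording change in the protocol and a small extra form burden per session. No additional staff are needed, and randomisation, endpoints and sample size do not change. Aligning the wording on a session-end survey alone would remove the inconsistency more cheaply, but it would repeat the opinion items needlessly and would not by itself link events to a patient or arm.
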